#### 13.3.2 Analysis of baseline demographic variables

Baseline descriptive statistics on all evaluable patients will be provided for demographic variables

NCI Protocol #: 9892

Version Date: January 12, 2023

(age, BMI, race/ethnicity), ECOG performance status, disease stage and status at the time of enrollment (stable disease, progressive disease), and treatment regimens previously used.

### 13.3.3 Analysis of Safety Endpoints

The NCI common terminology criteria for adverse events (CTCAE 5.0) will be used to evaluate toxicity; we will consider a toxicity to be an adverse event that is possibly, probably or definitely related to treatment. The rate of DLT at RP2D will be calculated and the exact 95% CI will be provided. The maximum grade of toxicity for each category of interest will be recorded for each patient and the summary results will be tabulated by category and grade. We will describe all DLTs and other serious ( $\geq$  Grade 3) adverse events on a patient-by-patient basis; descriptions will include dose level and any relevant baseline data. Statistics on the number of cycles received by patients and any dose reductions will also be tabulated.

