**Adverse Events by Frequency during the dose escalation of NCI 9892.**

AEFamily	AETerm	Grade1	Grade2	Grade3	Grade4	Total
GENERAL/ADM. SITE CONDITIONS	Fatigue	7 (70%)	3 (30%)			10 (100.0%)
GI DISORDERS	Nausea	10 (100%)				10 (100.0%)
BLOOD/LYMPH DISORDERS	Anemia		4 (40%)	5 (50%)		9 (90.0%)
GI DISORDERS	Diarrhea	7 (70%)	2 (20%)			9 (90.0%)
INVESTIGATIONS	Lymphocyte count decreased		1 (10%)	5 (50%)	3 (30%)	9 (90.0%)
METABOLISM & NUTRITION	Hypomagnesemia	6 (60%)	1 (10%)			7 (70.0%)
METABOLISM & NUTRITION	Hyponatremia	6 (60%)		1 (10%)		7 (70.0%)
INVESTIGATIONS	Neutrophil count decreased	2 (20%)		3 (30%)	2 (20%)	7 (70.0%)
INVESTIGATIONS	White blood cell decreased		2 (20%)	3 (30%)	2 (20%)	7 (70.0%)
BLOOD/LYMPH DISORDERS	Blood/Lymph - Other - Methemoglobinemia	1 (10%)	4 (40%)	1 (10%)		6 (60.0%)
INVESTIGATIONS	Platelet count decreased	3 (30%)	2 (20%)	1 (10%)		6 (60.0%)
RENAL & URINARY DISORDERS	Urinary frequency	5 (50%)	1 (10%)			6 (60.0%)
GI DISORDERS	Gastroesophageal reflux disease	2 (20%)	3 (30%)			5 (50.0%)
METABOLISM & NUTRITION	Hypocalcemia	5 (50%)				5 (50.0%)
EAR & LABYRINTH	Tinnitus	5 (50%)				5 (50.0%)
GI DISORDERS	Vomiting	5 (50%)				5 (50.0%)
GI DISORDERS	Constipation	4 (40%)				4 (40.0%)
RENAL & URINARY DISORDERS	Hematuria	3 (30%)	1 (10%)			4 (40.0%)
METABOLISM & NUTRITION	Hyperglycemia	4 (40%)				4 (40.0%)
METABOLISM & NUTRITION	Hypokalemia	3 (30%)		1 (10%)		4 (40.0%)
METABOLISM & NUTRITION	Anorexia	3 (30%)				3 (30.0%)
GI DISORDERS	Bloating	3 (30%)				3 (30.0%)
NERVOUS SYSTEM	Dizziness	3 (30%)				3 (30.0%)
RESPIRATORY/THORACIC/MEDIASTINAL	Dyspnea	2 (20%)	1 (10%)			3 (30.0%)
GENERAL/ADM. SITE CONDITIONS	Fever	2 (20%)	1 (10%)			3 (30.0%)
NERVOUS SYSTEM	Headache	3 (30%)				3 (30.0%)
VASCULAR DISORDERS	Hypertension	1 (10%)	1 (10%)	1 (10%)		3 (30.0%)
PSYCHIATRIC DISORDERS	Insomnia	3 (30%)				3 (30.0%)
RENAL & URINARY DISORDERS	Renal & urinary disorders - Other - Dysuria	3 (30%)				3 (30.0%)
GI DISORDERS	Abdominal pain	1 (10%)	1 (10%)			2 (20.0%)
BLOOD/LYMPH DISORDERS	Blood/Lymph - Other - Thrombocytopenia	2 (20%)				2 (20.0%)
METABOLISM & NUTRITION	Dehydration		2 (20%)			2 (20.0%)
GENERAL/ADM. SITE CONDITIONS	Edema limbs	2 (20%)				2 (20.0%)
MUSCULOSKELETAL/CONNECTIVE TISSUE	Generalized muscle weakness	2 (20%)				2 (20.0%)
METABOLISM & NUTRITION	Hypoalbuminemia	2 (20%)				2 (20.0%)

[figure not shown]
INVESTIGATIONS	Investigations - Other, specify - Fogginess	2 (20%)				2 (20.0%)
CARDIAC DISORDERS	Sinus tachycardia	1 (10%)	1 (10%)			2 (20.0%)

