MUSCULOSKELETAL/CONNECTIVE TISSUE	Pain in extremity	1 (10%)				1 (10.0%)
REPRODUCTIVE & BREAST DISORDERS	Pelvic pain	1 (10%)				1 (10.0%)
NERVOUS SYSTEM	Peripheral sensory neuropathy	1 (10%)				1 (10.0%)
RESPIRATORY/THORACIC/MEDIASTINAL	Productive cough	1 (10%)				1 (10.0%)
RENAL & URINARY DISORDERS	Proteinuria	1 (10%)				1 (10.0%)
RENAL & URINARY DISORDERS	Renal & urinary disorders - Other - Bladder Pain	1 (10%)				1 (10.0%)
RENAL & URINARY DISORDERS	Renal & urinary disorders - Other - Pyelonephritis			1 (10%)		1 (10.0%)
RENAL & URINARY DISORDERS	Renal & urinary disorders - Other - Urinary Pressure	1 (10%)				1 (10.0%)
REPRODUCTIVE & BREAST DISORDERS	Reproductive and breast - Other - Dysuria	1 (10%)				1 (10.0%)
REPRODUCTIVE & BREAST DISORDERS	Reproductive and breast - Other - Vaginal Bleeding	1 (10%)				1 (10.0%)
PSYCHIATRIC DISORDERS	Restlessness	1 (10%)				1 (10.0%)
SKIN & SUBCUTANEOUS DISORDERS	Skin & subcutaneous tissue -Other - Dermatitis	1 (10%)				1 (10.0%)
SKIN & SUBCUTANEOUS DISORDERS	Skin & subcutaneous tissue -Other - Parasthesia		1 (10%)			1 (10.0%)
SKIN & SUBCUTANEOUS DISORDERS	Skin & subcutaneous tissue -Other - Skin Patches	1 (10%)				1 (10.0%)
RESPIRATORY/THORACIC/MEDIASTINAL	Sore throat	1 (10%)				1 (10.0%)
GI DISORDERS	Toothache	1 (10%)				1 (10.0%)
RENAL & URINARY DISORDERS	Urinary incontinence	1 (10%)				1 (10.0%)
INJURY, POISONING & PROCEDURAL	Vascular access complication			1 (10%)		1 (10.0%)

Looking only at the highest grade for each Adverse Event experienced by a Patient, this report displays the number of patients that experienced each Adverse Event, by Grade, for each Organ Class and for each Preferred Term within an Organ Class. It also displays the percentage of treated patients in the study that experienced the Adverse Event with that Grade as their highest grade for that event.

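### The only planned safety table by category and grade counts related events alone, so Grade 1–2 events judged unlikely or unrelated appear in no planned summary

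*Combined protocol and SAP*

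**What the plan says.** Section 13.3.3 (Analysis of Safety Endpoints) contains three statements that matter here.

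- Definition: "we will consider a toxicity to be an adverse event that is possibly, probably or definitely related to treatment".
- Summary table, which is also split by grade: "The maximum grade of toxicity for each category of interest will be recorded for each patient and the summary results will be tabulated by category".
- Individual descriptions: all DLTs are to be described, together with "other serious ( $\geq$ Grade 3) adverse events on a patient-by-patient basis; descriptions will include dose level and any relevant baseline data".

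The first two use the word toxicity, which the section has just restricted to related events. The third uses adverse events and carries no such restriction.

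Section 7.2 defines a five-level attribution scale, in which relatedness is to the study treatment as a whole. Section 7.4 requires every adverse event to be submitted in routine reporting, whatever its attribution. Section 13.3.1 defines the safety set as all evaluable patients who start study treatment, so it covers escalation and expansion together.

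Section 5.1.3 already prints a table for the escalation phase, titled "Adverse Events by Frequency during the dose escalation of NCI 9892". Its note says that "this report displays the number of patients that experienced each Adverse Event, by Grade, for each Organ Class and for each Preferred Term". It adds: "It also displays the percentage of treated patients in the study that experienced the Adverse Event with that Grade as their highest grade". Neither the title nor the note mentions attribution.

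**The concern.** With no control group, no background rate is available against which to test whether an event was correctly called unrelated. A table restricted to related events therefore carries the attribution judgments into every rate it reports, and a reader cannot undo that without the all-event counts.

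This matters most for lower-grade events. The non-HIV+ expansion cohort of 12 exists partly to supply more safety information at the recommended dose (Sections 5.4.1 and 13.1.1). Much of what patients experience on this regimen is Grade 1 or 2, and for those events the related-only table is the sole planned summary. Urinary frequency, vaginal hemorrhage and pelvic pain, all seen in escalation, could plausibly be ascribed either to treatment or to the tumor. That is my inference; the documents do not attribute individual events.

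A second risk is presentational. A reader holding the escalation table and the final table might take a difference between them as a change in safety, when the two may not count the same things.

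**Working it through.** **1. What each planned output in 13.3.3 covers.**

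| Event | Category-by-grade table | Patient-by-patient description |
|---|---|---|
| Related, Grade 1–2 | Yes | No, unless a DLT |
| Related, Grade 3 or higher | Yes | Yes |
| Unlikely or unrelated, Grade 1–2 | No | No |
| Unlikely or unrelated, Grade 3 or higher | No | Yes (no filter stated) |

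The third row is the gap. The fourth row is reported, but as descriptions rather than rates.

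**2. Reproducing the escalation table.** One patient is shown as 10%, so N = 10. Adding the maximum-grade columns:

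- Anemia: 4 + 5 = 9, and 9/10 = 90%.
- Lymphocyte count decreased: 1 + 5 + 3 = 9, and 9/10 = 90%.

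Both agree with the printed totals.

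**3. How much of it is Grade 1–2 only.**

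- Fatigue: 7 + 3 = 10 of 10.
- Nausea: 10 of 10.
- Diarrhea: 7 + 2 = 9 of 10.
- Urinary frequency: 5 + 1 = 6 of 10.

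None of these has a Grade 3 or 4 entry, so the patient-by-patient description would add nothing on them.

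**4. Direction and size.** Let p be the all-event rate for a term, and q the share of affected patients with at least one such event called related. The related-only any-grade rate is q × p, which cannot exceed p. The same holds for the rate at or above any grade. A single grade cell can move either way: a patient with an unrelated Grade 2 and a related Grade 1 event of the same term moves into the Grade 1 cell.

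The documents give no value of q. Purely as an assumption, over a range:

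| q (assumed) | Anemia, p = 90% | Urinary frequency, p = 60% |
|---|---|---|
| 1.00 | 90% | 60% |
| 0.90 | 81% | 54% |
| 0.75 | 68% | 45% |
| 0.50 | 45% | 30% |

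At q = 1 nothing changes. The exact 95% interval for 6/10 is 26.2% to 87.8%, so even the lowest urinary-frequency figure lies inside the sampling uncertainty.

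**5. Is a relatedness effect already visible?** The text of 5.1.3 describes toxicity in nine evaluable patients; the table describes adverse events in ten treated patients. For Grade 3–4:

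| Term | Text (of 9) | Table (of 10) |
|---|---|---|
| Lymphocytes | 7 | 5 + 3 = 8 |
| Anemia | 4 | 5 |
| Neutrophils | 4 | 3 + 2 = 5 |
| White cells | 4 | 3 + 2 = 5 |
| Platelets, hypertension, hyponatremia | 1 each | 1 each |

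The different denominators, and the framing of the text as events apart from the DLTs, can explain these gaps. They do not show an attribution effect.

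**6. Other differences between the two tables.** The pharmacokinetic tables in 5.1.3.3 list 6 patients at 100 mg and 4 at 150 mg, and 6 + 4 = 10, which matches the adverse event table. That table therefore pools dose levels, while expansion is at 100 mg only. Section 5.1.3.6 counts 6 + 3 = 9 evaluable patients.

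**The case against.** Much of the case on the other side stands.

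- **The safety set is not expansion-only.** The final table will apply one rule to escalation and expansion patients alike, and no section plans to compare the 5.1.3 table with expansion rates. A reader might infer that the phases cannot be compared at all. The documents do not support that: all events are collected and an attribution scale exists, so both phases can be tabulated on either basis.
- **Severe events are not hidden.** Those of Grade 3 or higher are to be described without a stated filter.
- **Rates need not fall.** A reader might infer that expansion rates will look lower, or that every rate is biased downward. Because attribution is to the whole regimen of cisplatin, pelvic radiation and triapine, common cytopenias and gastrointestinal events may lose few cases or none.
- **All-event counting in escalation is the natural reading, not a stated rule.** Rows such as toothache and sore throat point that way, but the note does not say that attribution was ignored.
- **The dose decision does not turn on this table.** Section 5.1.3.6 bases the MTD on DLT counts, 1 of 6 against 2 of 3. DLT uses the same relatedness rule in both phases (Section 5.5).

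None of this supplies a planned summary of Grade 1–2 events judged unlikely or unrelated. That part is unanswered.

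**Conclusion.** The point holds in a narrow form. The only planned category-by-grade table depends on attribution in a trial with no control group, and one class of events is left out of every planned summary. The any-grade rates it yields will equal or fall below the all-event rates by an amount that cannot be computed from the documents and may be zero. The percentages in the working for q below 1 are illustrations under an assumed range, not estimates.

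The escalation table should not be read against the final table unless three differences are stated: the counting rule, the pooled dose levels and the denominator. This rests on reading toxicity in the tabulation sentence as defined two sentences before it, and on taking the escalation table's silence on attribution as the absence of a filter.

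The DLT rate and its exact interval, the stopping rule and the sample size are unaffected. This is a minor reporting improvement.

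**What to change.** In 13.3.3, make the main table the maximum grade by category for all adverse events regardless of attribution, with the related subset beside it. Present it by dose level for every patient in the safety set, on one labelled denominator. Keep relatedness for DLT exactly as Section 5.5 has it. If the escalation table from 5.1.3 is reproduced in the final report, either rebuild it on the same basis or footnote its counting rule, pooled dose levels and ten-patient denominator.

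The cost is one extra table or column. Section 7.4 already requires all adverse events to be submitted and Section 7.2 already defines the attribution scale, so no new data are needed. The one drawback is that the reported rates may be somewhat higher.

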## 6.6 Methemoglobinemia

If patients had prolonged methemoglobinemia or hypoxia requiring dose adjustment during any of the observation periods noted in the table above (5.3.3.1 Clinical Monitoring for Methemoglobin), follow the schema until stable.

Please note, it is the *trend* in the O2 saturation that is of importance. Since pulse oximetry is known to be unreliable in the presence of significant methemoglobinemia, weight should not be given to a single value alone. In any case where there is significant doubt, serial spot methemoglobin should be obtained (as clinically indicated based on symptoms such as but not limited to skin discoloration, cyanosis, coma, or dysrhythmia and levels can be repeated every 6-8 hours until levels <20%) and consultation as needed.

It is expected that all patients will show a transient rise in methemoglobin (up to 10-15%) while on study but unless accompanied by hypoxia, or symptoms (e.g., dyspnea), no changes to treatment or dose may be required. However, for patients not fitting this pattern, the following guidelines should be followed:

- If methemoglobin is asymptomatic, <20%, and NOT accompanied by hypoxia (oxygen saturation <92%) : treat without change in dose.
- IF methemoglobin >15% lasts more than 3 hours OR if methemoglobin >20% OR if oxygen saturation <92%, THEN: obtain arterial blood gases (a pO2 <80 should result in hospitalization and will be counted as DLT). If pO2 normalizes within 24 hours, retreatment at a lower dose level may be considered by the Principal Investigator at UPCI.

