### Phase 1 and Early Phase 2 Studies: Expedited Reporting Requirements for Adverse Events that Occur on Studies under an IND/IDE within 30 Days of the Last Administration of the Investigational Agent/Intervention 

#### FDA REPORTING REQUIREMENTS FOR SERIOUS ADVERSE EVENTS (21 CFR Part 312)

**NOTE:** Investigators **MUST** immediately report to the sponsor (NCI) **ANY** Serious Adverse Events, whether or not they are considered related to the investigational agent(s)/intervention (21 CFR 312.64)

An adverse event is considered serious if it results in **ANY** of the following outcomes:

- 1) Death
- 2) A life-threatening adverse event
- 3) An adverse event that results in inpatient hospitalization or prolongation of existing hospitalization for ≥ 24 hours
- 4) A persistent or significant incapacity or substantial disruption of the ability to conduct normal life functions
- 5) A congenital anomaly/birth defect.

6) Important Medical Events (IME) that may not result in death, be life threatening, or require hospitalization may be considered serious when, based upon medical judgment, they may jeopardize the patient or subject and may require medical or surgical intervention to prevent one of the outcomes listed in this definition. (FDA, 21 CFR 312.32; ICH E2A and ICH E6).		
ALL SERIOUS adverse events that meet the above criteria MUST be immediately reported to the NCI via electronic submission within the timeframes detailed in the table below.		
Hospitalization	Grade 1 and Grade 2 Timeframes	Grade 3-5 Timeframes
Resulting in Hospitalization $\geq 24$ hrs	10 Calendar Days	24-Hour 5 Calendar Days
Not resulting in Hospitalization $\geq 24$ hrs	Not required	

NOTE: Protocol specific exceptions to expedited reporting of serious adverse events are found in the Specific Protocol Exceptions to Expedited Reporting (SPEER) portion of the CAEPR.
 
Expedited AE reporting timelines are defined as:
 
 
○ “24-Hour; 5 Calendar Days” - The AE must initially be submitted electronically within 24 hours of learning of the AE, followed by a complete expedited report within 5 calendar days of the initial 24-hour report.
 
○ “10 Calendar Days” - A complete expedited report on the AE must be submitted electronically within 10 calendar days of learning of the AE.
 
		

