
Serious adverse events that occur more than 30 days after the last administration of investigational agent/intervention and have an attribution of possible, probable, or definite require reporting as follows:
 
Expedited 24-hour notification followed by complete report within 5 calendar days for:
 
 
• All Grade 3, 4, and Grade 5 AEs
 
 
Expedited 10 calendar day reports for:
 
 
• Grade 2 AEs resulting in hospitalization or prolongation of hospitalization
 
 
For studies using PET or SPECT IND agents, the AE reporting period is limited to 10 radioactive half-lives, rounded UP to the nearest whole day, after the agent/intervention was last administered. Footnote “1” above applies after this reporting period.
 
Effective Date: May 5, 2011
		

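### Section 13.3.3 uses 'serious' to mean Grade 3 or higher, against the outcome-based definition in 7.3.3, so the patient-level safety description omits serious Grade 1-2 events that are not DLTs

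*Combined protocol and SAP*

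**What the plan says.** Section 13.3.3 (Analysis of Safety Endpoints) plans three outputs:

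- a DLT rate at the RP2D with an exact 95% interval;
- a table by category and grade, for which "The maximum grade of toxicity for each category of interest will be recorded for each patient";
- individual descriptions: "We will describe all DLTs and other serious", then a parenthesis setting the threshold at Grade 3 or above, then "adverse events on a patient-by-patient basis; descriptions will include dose level and any relevant baseline data".

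The same section defines a toxicity as an adverse event at least possibly related to treatment.

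Section 7.3.3 (Expedited Reporting Guidelines) defines the word differently: "An adverse event is considered serious if it results in" one of six outcomes. These are death, a threat to life, hospitalisation, incapacity, a congenital anomaly, or an important medical event. The hospitalisation criterion reads "An adverse event that results in inpatient hospitalization or prolongation of existing hospitalization for ≥ 24 hours" and names no grade. The table there gives Grade 1 and Grade 2 events with such a hospitalisation a timeline of "10 Calendar Days". For related events more than 30 days after the last dose, the footnote still asks for a report of "Grade 2 AEs resulting in hospitalization or prolongation of hospitalization".

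Section 6.6 (Methemoglobinemia) says that a pO2 below 80 "should result in hospitalization and will be counted as DLT".

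**The concern.** The two sections give one word two meanings. CTCAE grade measures severity, whereas 7.3.3 asks what happened to the patient. An analyst who follows 13.3.3 would select cases by grade. A patient admitted for a Grade 2 event would get no individual description unless the event was also a DLT, while a patient with a Grade 3 lymphocyte count and no clinical consequence would be described as having had a serious event.

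At stake is the clarity of the safety account for the expansion cohorts: 12 non-HIV+ patients and up to 28 HIV+ patients, so up to 12 + 28 = 40. Section 13.2.1 gives further definition of the range of toxicities as a reason for enrolling the 12. Section 13 contains no other listing or tabulation of serious adverse events that would fill the gap.

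**Working it through.** This is a check of definitions. The plan gives no figure to reproduce, and no error rate or sample size is involved.

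**1. Apply both definitions to the same events.** The parenthesis in 13.3.3 can be read as a gloss (serious means Grade 3 or higher) or as a restriction (serious and also Grade 3 or higher). The gloss is the plain reading.

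| Event | Serious under 7.3.3 | Described under 13.3.3, gloss | Described under 13.3.3, restriction |
|---|---|---|---|
| Grade 1-2, hospitalised 24 h or more, not a DLT | Yes | No | No |
| Grade 1-2, hospitalised 24 h or more, also a DLT | Yes | Yes, as a DLT | Yes, as a DLT |
| Grade 3 laboratory value, no serious outcome, not a DLT | No | Yes, and called serious | No |
| Grade 3 or higher with a serious outcome | Yes | Yes | Yes |

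The omission in the first row holds on either reading. The mislabelling in the third row holds only on the gloss.

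**2. Look for the omitted event elsewhere in Section 13.** The maximum-grade table carries no seriousness flag, and it covers toxicities, meaning related events only. A related Grade 2 hospitalisation would appear there as an ordinary Grade 2 count. One judged unrelated would appear in no Section 13 output.

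**3. Look for it in expedited reporting.** Section 7.1.1.1 lists SPEER grades, including methemoglobinemia (Grade 2), dehydration (Grade 2), fever (Grade 2) and infection (Grade 3). Listed events are reported only if they exceed that grade, and a note in 7.3.3 applies these exceptions to serious events. A hospitalised Grade 2 methemoglobinemia can therefore be exempt from CTEP-AERS. Section 7.4 still requires it in routine Rave data.

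**4. Size of the mislabelling, from the dose-escalation adverse event table in 5.1.3 (10 treated patients).**

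- Lymphocyte count decreased: worst grade 3 in 5 patients and worst grade 4 in 3. Section 5.5 sets the hematologic DLT threshold at Grade 4, so the 5/10 at Grade 3 are not DLTs by grade. The 3/10 at Grade 4 may already be DLTs if at least possibly related.
- All Grade 3-4 entries: 25 at Grade 3 + 7 at Grade 4 = 32.
- Blood-count entries among them: anemia 5 + lymphocytes 8 + neutrophils 5 + white cells 5 + platelets 1 = 24, and 24/32 = 75%.
- Blood-count entries at Grade 3 only: 5 + 5 + 3 + 3 + 1 = 17, and 17/32 = 53%.

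These are patient-by-term entries, so one patient can contribute several. The table does not show which met a 7.3.3 outcome.

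**5. Size of the omission.** The table records grade and not hospitalisation, so this cannot be computed. Methemoglobin shows only that the relevant grade is common: the seven differently worded rows hold 6 + 6 = 12 entries, of which 4 + 6 = 10 are Grade 2. Entries in different rows may come from the same patient, and none shows a hospitalisation.

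**The case against.** The strongest reply is that nothing is lost. Hospitalised Grade 1-2 events have their own expedited timeline, expedited events must also enter routine data, and Section 12.1 has the Principal Investigator review serious events, with at least monthly calls with CTEP in the Phase 1 portion. This stands as far as data capture goes. It does not close the gap, because those are reporting and oversight channels and not the planned analysis, and because the SPEER exceptions can remove some of these events from the expedited route.

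A second reply is that the parenthesis is loose usage for severe, or a restriction, and tells the analyst exactly what to list. On the restriction reading the mislabelling disappears. The omission remains either way.

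A third reply concerns methemoglobin. A reader might infer that hospitalised Grade 2 cases outside the DLT window would go undescribed. The documents do not support that example. The window runs to the end of EBRT (5.5), oral triapine is given only on radiation days up to that point (5.3.3), and its half-life in this trial was 1.3 to 1.5 hours (5.1.3.3), so acute events should fall almost wholly inside the window. The one hospitalisation trigger stated for methemoglobin, pO2 below 80, already counts as a DLT, and 13.3.3 describes all DLTs. What is left is a Grade 2 case admitted with pO2 of 80 or above that is not a DLT on other grounds, such as missed doses. That is possible on the text, but no such case is shown.

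**Conclusion.** Wrong as written, low severity. Section 13.3.3 contradicts 7.3.3 on the meaning of serious. On either reading of the parenthesis, the patient-by-patient description omits Grade 1-2 events that meet 7.3.3 and are not DLTs. On the plain reading it also calls non-serious Grade 3 laboratory values serious. The clean illustration is the 5 of 10 escalation patients whose worst lymphopenia was Grade 3, on the assumption that those values led to no 7.3.3 outcome. The number of omitted events is unknown.

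Three larger conclusions that a reader might draw are not supported:

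- **That the RP2D or safety stopping is compromised.** The RP2D rule (5.1.2) and the Bayesian suspension rule (13.1.1) use DLTs only, and the expansion dose has already been chosen (5.1.3). No decision rule, error rate or sample size depends on these descriptions.
- **That 80% of escalation patients would be mislabelled.** The 8 of 10 with Grade 3 or 4 lymphopenia include 3 at Grade 4 who may be described as DLTs in any case.
- **That a serious-event rate would conflict with CTEP-AERS.** Section 13.3.3 plans no such rate.

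The effect is confined to how the safety of the expansion patients is described.

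**What to change.** Replace the sentence in 13.3.3 so that the plan describes patient by patient (a) all DLTs, (b) all serious adverse events as defined in 7.3.3, at any grade and whatever the attribution, and (c) separately, all severe adverse events, meaning Grade 3 or higher. Tabulate (b) and (c) as two separate counts, and use severe wherever grade is meant.

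The cost is one sentence and a little extra listing work. It needs no new visits or samples. The events are already required in Rave, so the listing should be drawn from there and not from CTEP-AERS alone, since SPEER-exempt events may be missing from the latter.
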